4.2.2. Exclusion Criteria

Deviations from exclusion criteria are not allowed because they can potentially jeopardize the scientific integrity of the study, regulatory acceptability or subject safety. Therefore, adherence to the criteria as specified in the protocol is essential.

Subjects meeting any of the following criteria must not be enrolled in the study:

Safety

1. The subject has a mixed malaria infection (identified by a malarial smear or rapid diagnostic test).
2. The subject has severe *P. vivax* malaria as defined by WHO criteria.
3. The subject has a history of allergy to chloroquine, mefloquine, tafenoquine, primaquine, or to any other 4- or 8-aminoquinoline.

Hepatic Disease

4. The subject has a liver ALT >2 x ULN.

Concurrent Disease

5. The subject has severe vomiting (no food or inability to take food during the previous 8 hours).
6. The subject has a clinically significant concurrent illness (e.g., pneumonia, septicemia), pre-existing condition (e.g., renal disease, malignancy), condition that

may affect absorption of study medication (e.g., vomiting, severe diarrhea), or clinical signs and symptoms of severe cardiovascular disease (e.g., uncontrolled congestive heart failure, severe coronary artery disease).

7. The subject has a history of porphyria, psoriasis, or epilepsy.
8. The subject has a history of significant ocular disease (e.g. surgery to the globe, glaucoma, diabetic retinopathy) or has evidence of corneal or retinal abnormalities identified in the clinical screening ophthalmologic examination.

Concurrent Medication

9. The subject has taken anti-malarials (e.g., artemisinin-based combination therapies, mefloquine, primaquine, or any other 4- or 8-aminoquinoline) within 30 days prior to study entry.
10. The subject has taken or will likely require during the study the use of medications from the following classes:

- Histamine-2 blockers and antacids
- Drugs with hemolytic potential
- Drugs known to prolong the QTcF interval
- The biguanides phenformin and buformin (but excluding metformin)
- Drugs that are substrates of the renal transporters OCT2, MATE1 and MATE-2K and have a narrow therapeutic index (for example, the anti-arrhythmic agents dofetilide, procainamide and pilsicainide)

Other

11. The subject has received treatment with any investigational drug within 30 days of study entry, or within 5 half-lives, whichever is longer.
12. The subject has a recent history of illicit drug abuse or heavy alcohol intake, such that full participation in the study could be compromised.

NOTES ON ELIGIBILITY CRITERIA:

- See [Appendix 4](#) (Section 11.4) for the WHO definition of severe malaria.
- Ophthalmic safety assessments will only be conducted at appropriately qualified investigator sites. Therefore, exclusion criterion 8 only applies to those pre-selected sites. A subject may be excluded from the ophthalmic assessments at one of these sites but still participate in the main portion of the study.
- For centers participating in this study and sister Study TAF112582: if female subjects screen fail Study TAF112582 due to being G6PD deficient, they may enrol in this study using the screening labs and procedures from the TAF112582 screening process.

4.3. Withdrawal Criteria

- Adverse event
- Protocol deviation
- Study closed/terminated
- Lost to follow-up
- Consent withdrawal
- Subject or investigator non-compliance
- At the request of the subject, investigator, or sponsor
- Pregnancy

A subject may voluntarily discontinue participation in this study at any time. The investigator may also, at their discretion, discontinue the subject from participating in this study at any time. A subject is considered to be withdrawn prematurely from the study if they do not complete the Day 180 assessment. A subject may withdraw or be prematurely withdrawn for any of the reasons presented in the list above. If a subject withdraws consent the site should offer to conduct safety assessments through Day 90.

Subjects are not obligated to state the reason for withdrawal from this study. However, the reasons for withdrawal, or failure to provide a reason, must be documented by the investigator on the Completion/Withdrawal section of the electronic Case Record Form (eCRF). If a subject is withdrawn from the study for any reason, the investigator must make every effort to perform the study evaluations as specified in [Table 2](#) for the Relapse or Withdrawal visit as applicable.

4.4. Premature Withdrawal of Study Medication

If a subject prematurely discontinues from blinded study medication, the reason for withdrawal from medication should be recorded in the eCRF. As useful safety and efficacy information can still be obtained for these patients, the investigator should continue following subjects for all protocol assessments, up to and including day 180. The subject should be offered/given appropriate rescue medication as detailed in [Section 5.6.1.2](#) if they get a recurrence of malaria due to inability to take blinded study medication.

Subjects who withdraw from open label CQ (and prior to receiving blinded study medication) will not continue in the study and should be offered alternative treatment in accordance with site (local) or national treatment guidelines for *P. vivax* malaria. These subjects should be followed up until resolution of the malaria infection.

In addition, subjects should discontinue taking study medication if they meet any of the following criteria:

- Any grade 4 AE or toxicity in the absence of compelling evidence that the AE is not related to study medication

- Clinically significant laboratory results considered by the investigator to warrant withdrawal from the study
- QT stopping criteria as defined below:
 - QTcF > 500msec
 - Uncorrected QT > 600msec

These criteria should be based on the average QTcF value of triplicate ECGs. For example, if an ECG demonstrates a prolonged QT interval, obtain two more ECGs over a brief period, and then use the averaged QTcF values of the three ECGs to determine whether the patient should be discontinued from the study.

- For subjects with underlying Bundle Branch Block, the criterion is ≥ 530 msec.
- Liver chemistry stopping criteria as specified in Section 6.4.1
- Given the hemolytic potential of TQ and PQ in subjects with G6PD deficiency, study specific hemoglobin stopping criteria will be employed. Refer to Section 6.4.2 for details.

When QT or hematologic stopping criteria are met, this must be promptly reported by the investigator to GSK (see Section 6.4.11)

5. STUDY TREATMENTS

5.1. Investigational Product and Other Study Treatment

Throughout the protocol, study treatments will be defined and described as follows:

- "Study medication" refers to all drugs and placebos used in the study
- "Blinded study medication" refers to tafenoquine, primaquine and the corresponding placebos

The contents of the study medication labels will be in accordance with all applicable regulatory requirements. All study medication is being supplied by GlaxoSmithKline.

5.1.1. Tafenoquine

Tafenoquine will be supplied as a dark pink, 17.1mm × 9.0mm, capsule-shaped, film-coated tablet that is plain on both sides. Each tablet will contain 150mg tafenoquine.

5.1.2. Tafenoquine Placebo

Placebo tafenoquine tablets will be supplied as a dark pink, 17.1mm × 9.0mm, capsule-shaped, film-coated tablet that is plain on both sides, with common excipients of appropriate quality.

5.1.3. Chloroquine

One of two formulations of commercially available generic chloroquine may be utilized in this study:

1. tablets containing 500 mg chloroquine phosphate (equivalent to 300 mg chloroquine free base); or,
2. tablets containing 250 mg chloroquine phosphate (equivalent to 155 mg chloroquine free base).

5.1.4. Primaquine

Commercially available primaquine phosphate tablets containing primaquine phosphate 26.3 mg (equivalent to primaquine base 15 mg) over-encapsulated in a Swedish orange capsule will be utilized in this study.

5.1.5. Primaquine Placebo

Placebo to match primaquine will be supplied as Swedish orange capsules with common excipients of appropriate quality.

5.1.6. Handling and Storage of Investigational Product

Under normal conditions of handling and administration, investigational product is not expected to pose significant safety risks to site staff. A Material Safety Data Sheet (MSDS) describing the occupational hazards and recommended handling precautions will be provided to site staff if required by local laws or will otherwise be available from GSK upon request.

Investigational product must be stored in a secure area under the appropriate physical conditions for the product at a temperature up to 30°C (87°F). Access to and administration of the investigational product will be limited to the investigator and authorized site staff. Investigational product must be dispensed or administered only to subjects enrolled in the study and in accordance with the protocol.

A temperature log must be maintained at all study sites where study medication is stored.

Following full drug accountability, all used study medication should be destroyed at site according to local guidelines.

5.1.7. Duration of Treatment of Active Study Medication

The total duration of treatment is 15 days.

Chloroquine will be dosed orally once daily for three days starting on Day 1 of the study.

Tafenoquine will be dosed orally as a single dose on Day 1 or Day 2 of the study.

Primaquine will be given as a 14-dose course administered orally once daily for 14 days starting from Day 1 or Day 2 of the study.

5.1.8. Dose and Administration

Study medication should be administered with food. If the subject vomits within 1 hour following dosing, a repeat dose should be given. If a subject sequentially vomits two doses of study medication he/she will be considered intolerant to study medication. These subjects will be withdrawn from study medication and be given appropriate rescue medication as outlined in Section 5.6.1.2. Subjects and all site staff will be blinded to the study treatment.

Subjects will be randomized into one of two treatment arms. Subjects that receive the 500 mg CQ tablet (300 mg CQ free base) will receive the following number of CQ tablets, TQ/placebo tablets and PQ/placebo capsules:

Treatment Arm	Day 1	Day 2	Day 3	Days 4 – 15
tafenoquine	2×CQ 300mg	2×CQ 300mg + 2×TQ 150mg + 1×PQ placebo	1×CQ 300mg + 1×PQ placebo	1×PQ placebo
primaquine	2×CQ 300mg	2×CQ 300mg + 2×TQ placebo + 1×PQ 15mg	1×CQ 300mg + 1×PQ 15mg	1×PQ 15mg
Total number of capsules/tablets per treatment arm	2 tablets	4 tablets + 1 capsule	1 tablet + 1 capsule	1 capsule × 12 days

NOTE: subjects may begin blinded study medication (TQ or PQ and corresponding placebo) on Day 1 or Day 2 of the study.

Subjects that receive the 250 mg CQ tablet (155 mg CQ free base) will receive the following number of CQ tablets, TQ/placebo tablets and PQ/placebo capsules:

Treatment Arm	Day 1	Day 2	Day 3	Days 4 – 15
tafenoquine	4×CQ 155mg	4×CQ 155mg + 2×TQ 150mg + 1×PQ placebo	2×CQ 155mg + 1×PQ placebo	1×PQ placebo
primaquine	4×CQ 155mg	4×CQ 155mg + 2×TQ placebo + 1×PQ 15mg	2×CQ 155mg + 1×PQ 15mg	1×PQ 15mg
Total number of capsules/tablets per treatment arm	4 tablets	6 tablets + 1 capsule	2 tablet + 1 capsule	1 capsule × 12 days

NOTE: subjects may begin blinded study medication (TQ or PQ and corresponding placebo) on Day 1 or Day 2 of the study.

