3.3. Discussion of Design

The design of TAF116564 has been made purposely similar to Part 2 of sister study TAF112582, the pivotal phase III efficacy and safety study of the tafenoquine program.

The overall design of the studies is based on FDA guidance for the radical cure of malaria due to *P. vivax*. In this double-blind, double-dummy design, subjects will be screened and randomized to treatment on Day 1, and will remain in the hospital for the first 3 days of the study, or until two consecutive thick blood smears are negative for *P. vivax*, to monitor study medication compliance and infection status. Subjects will continue on treatment for the first 15 days of the study and will be monitored up to day 32 for recrudescence. Subjects will continue to be monitored up to 180 days post-randomization for evidence of relapsing infection. In all subjects, PCR analysis of *Plasmodium* species will be conducted to investigate the genetic constitution of *P. vivax* recurrences during the study.

All subjects will receive open label CQ for the first 3 days of the study to treat the blood stage of the infection. Beginning on Day 1 or Day 2, subjects will receive TQ or the active comparator, PQ, and the corresponding placebo for treatment of the liver stage of infection. Primaquine was selected as the comparator for this study as PQ plus CQ is the current standard of care for radical cure of *P. vivax* malaria in the majority of endemic countries.

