3.3.1. Dose Rationale

Tafenoquine has demonstrated preliminary efficacy following 1-3 days of dosing, which is further supported by a prolonged half-life of 15-19 days. This shorter course of therapy should significantly improve compliance and thus effectiveness of relapse prevention.

Two separate exploratory clinical studies have demonstrated TQ's utility for the treatment and radical cure of *P. vivax* malaria: Study SB-252263/047 [GlaxoSmithKline Document Number [RM2007/00309/00](#)] was conducted in two parts, and tafenoquine was administered following chloroquine treatment of blood schizonts. Tafenoquine was found to be highly efficacious across the entire 500 mg to 3000 mg dose range. In study SB-252263/058 [GlaxoSmithKline Document Number [UM2004/00017/00](#)], a total dose of 1200 mg tafenoquine was administered over 3 days. Tafenoquine resulted in 100% relapse prevention, however, the tafenoquine monotherapy regimen exhibited slow parasite and fever clearance times relative to the CQ+PQ control. In conclusion, TQ's long half-life supported a 1 to 3 day treatment regimen when co-administered with a second blood schizonticidal drug, such as CQ.

A two-part drug-drug interaction study [GlaxoSmithKline Document Number [WD2009/01503/00](#); Study TAF106491] has also been conducted to investigate the interaction between TQ and CQ in healthy volunteers. Part 1 was a three arm, open label pilot study to evaluate the safety and pharmacokinetics of a low dose CQ co-administered with TQ. Part 2 was a double-blind study to assess the drug-drug interaction, safety (including ECG effects), tolerability and pharmacokinetic parameters of CQ co-administered with TQ. Based on the PK results from the pivotal Part 2 portion of this study, there appears to be a short term significant effect on TQ PK (Day 2 Cmax and AUC(0-24)) when co-administered with CQ with no significant effect on the full PK profile (AUC(0-∞) and t1/2). TQ had no significant effect on the PK of CQ and desethylchloroquine. Taken together, these results suggest that there is no clinically significant pharmacokinetic interaction with concomitant administration of TQ and CQ.

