5.3. Blinding

This is a double-blind study and both subject and study staff will remain blinded to treatment.

The investigator or treating physician may unblind a subject's treatment assignment **only in the case of an emergency or in the event of a serious medical condition**, when knowledge of the study treatment is essential for the appropriate clinical management or welfare of the subject, as judged by the investigator. Investigators have direct access to the subject's individual study treatment. It is preferred (but not required) that the investigator first contacts the GSK Medical Monitor or appropriate GSK study personnel to discuss options **before** unblinding the subject's treatment assignment. If GSK study personnel are not contacted before the unblinding, the investigator must notify GSK as soon as possible, but without revealing the treatment assignment of the unblinded subject, unless that information is important for the safety of subjects currently in the study. The date and reason for the unblinding must be fully documented in the appropriate data collection tool.

GSK's Global Clinical Safety and Pharmacovigilance (GCSP) staff may unblind the treatment assignment for any subject with an SAE. If the SAE requires that an expedited regulatory report be sent to one or more regulatory agencies, a copy of the report,

identifying the subject's treatment assignment, may be sent to clinical investigators in accordance with local regulations and/or GSK policy.

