5.5. Treatment Compliance

Compliance with study medication will be assessed in all subjects by directly observing the taking of medication for days 1-3 of the study. Compliance with respect to PQ medication/placebo in the subgroup of female subjects with moderate G6PD deficiency will be assessed for days 4-15 also by directly observing the taking of study medication. In all other subjects, outpatient compliance will be assessed by pill count and will be evaluated using details of dose administration recorded in the eCRF.

As part of the assessment of PQ compliance, levels of PQ and 7-carboxy PQ will be measured on Days 2, 3, 8 and 15 using TQ pharmacokinetic samples (see Section 6 and Section 6.6.1). Refer to the SPM for detailed methodology on measuring PQ and 7-carboxy PQ in these samples.

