5.6.1.2. Rescue Medication

Subjects requiring rescue medication will be given appropriate medication in accordance with site (local) or national treatment guidelines for *P. vivax* malaria or; e.g., *P. falciparum* malaria, whichever is applicable. Subjects offered rescue medication should be followed up for safety assessment until resolution of the malaria infection.

Details of rescue medication including reason for the rescue medication offered (e.g. withdrawal from study, treatment failure) should be recorded in the eCRF.

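### Protocol 5.1.8 sends subjects who vomit two doses to rescue even if the single TQ dose was kept, so a blinded site could add primaquine to it

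*Supplement*

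**What the plan says.** All references are to Protocol Amendment 5 unless the RAP (Amendment 1) is named.

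- **Trigger and consequence (5.1.8).** A dose vomited within an hour is repeated. A subject who vomits two doses in sequence is classed as intolerant, and then: "These subjects will be withdrawn from study medication and be given appropriate rescue medication as outlined in Section 5.6.1.2".
- **Scope (5.1).** Study medication "refers to all drugs and placebos used in the study". The rule therefore covers CQ tablets and PQ or PQ-placebo capsules as well as the TQ tablets.
- **Timing (5.1.7).** TQ is one dose on Day 1 or Day 2. CQ runs to Day 3, and the capsules run for 14 days.
- **Rescue (5.6.1.2).** Subjects "will be given appropriate medication in accordance with site (local) or national treatment guidelines". No drug is named and none is excluded. Follow-up is until the infection resolves.
- **What local practice usually is (3.3).** The reason given for the comparator is that "PQ plus CQ is the current standard of care for radical cure" in most endemic countries.
- **A different rule (4.4).** After stopping blinded medication, rescue is given "if they get a recurrence of malaria due to inability to take blinded study medication", and follow-up continues to Day 180.
- **Blinding (5.1.8, 5.3).** Site staff are blinded. A code break is reserved for an emergency or serious medical condition, and it is "preferred (but not required) that the investigator first contacts the GSK Medical Monitor".
- **Interaction note (Appendix 5).** PQ is listed as contraindicated with other potentially haemolytic drugs.

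**The concern.** The right rescue depends on two facts that 5.1.8 never asks for: whether the TQ/TQ-placebo tablets were kept, and which arm the subject is in. A TQ subject who kept the tablets has already had the whole radical-cure dose, so PQ would be a second 8-aminoquinoline. A PQ subject who can no longer take the capsules needs PQ, or an equivalent, to finish radical cure. A blinded site cannot tell the two apart.

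The stake is safety, mainly in moderately G6PD-deficient females. Section 3.3.1 reports that 300 mg TQ alone produced haemoglobin declines in such healthy volunteers similar to those on daily 15 mg PQ. Section 8.2.1 assumes that half of heterozygous females meet the haemolysis endpoint on either drug. These women also have their capsules directly observed throughout: their compliance "will be assessed for days 4-15 also by directly observing the taking of study medication" (5.5).

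There is also a small reporting issue. RAP 13.6.3 counts a qualifying haemoglobin fall at any visit after first dose, with no marker for a fall that follows rescue. RAP 13.6.4 does take anti-malarial use into account for relapse.

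**Working it through.** The plan gives no figure for this point, so the check is mostly a comparison of rules, with some side arithmetic.

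**1. Can the rule fire with TQ retained?** Capsule days after the TQ day:
- Blinded start on Day 2: Days 3 to 15 = 13 days.
- Blinded start on Day 1: Days 2 to 14 = 13 days.

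On each of these days the TQ tablets have already been given. Of the 13, direct observation covers 1 (start Day 2) or 2 (start Day 1) in most subjects, and all 13 in moderately deficient females (5.5). Section 5.5 concerns the taking of the dose; it does not say staff watch for the following hour. These counts show when the rule can apply, not how often it will.

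**2. How much TQ would still be present?** Section 3.3.1 gives "a prolonged half-life of 15-19 days". Assuming first-order decline and ignoring absorption, the fraction left after d days with half-life h is 0.5^(d/h).

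| d (days after TQ) | h = 15 | h = 19 |
|---|---|---|
| 1 | 95.5% | 96.4% |
| 2 | 91.2% | 93.0% |
| 6 (Day 8 if TQ on Day 2) | 75.8% | 80.3% |
| 13 (Day 15 if TQ on Day 2) | 54.8% | 62.2% |

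This shows overlap in exposure. It does not measure added haemolysis.

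**3. What would be added?** If the local guideline were the PQ regimen in this protocol (an assumption), rescue would be 15 mg x 14 = 210 mg PQ.

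**4. Is some rescue needed?** A lost Day 3 dose includes 300/1500 = 20% of the CQ course (310/1550 = 20% with the 155 mg tablet). Replacing lost CQ is right. Only the 8-aminoquinoline is in question.

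**5. How many people?** The documents give no frequency of double vomiting. The planned minimum of 50 moderately deficient females at 2:1 would put 50 x 2/3 = about 33 on TQ, but RAP 2.1 says this subgroup will be limited in number. With 251 randomised (meta-analysis plan, section 3), the TQ arm is about 251 x 2/3 = 167. One haemolysis event would be 1/167 = 0.6 percentage points.

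**6. Do other sections settle it?**
- 4.4 and 5.1.8 give different conditions for rescue, and neither says which prevails. Follow-up also differs: Day 180 in 4.4, resolution of infection in 5.6.1.2.
- 5.6.2 prohibits haemolytic drugs through Day 180, but in the same list prohibits anti-malarials. Read literally it would forbid rescue altogether, so it cannot be the rule that selects the rescue drug.
- 5.3 allows investigators to break the code only in an emergency or serious condition. A repeatedly vomited capsule is not clearly either.

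**The case against.** The strongest reply is that the path to harm runs through guidelines nobody here can see. Section 5.6.1.2 names no drug and asks for appropriate treatment. The site knows each subject's quantitative G6PD result from Day 1 (3.2, 4.2.1), and nothing in the documents says a local guideline would give daily PQ to a woman known to be deficient. On Days 4-15 only the blinded capsule is taken, and 4.4 can be read as saying wait for recurrence. Haemoglobin is checked on Days 3, 5, 8, 11, 15, 22 and 29, a qualifying fall in the first 15 days is a protocol-defined SAE (6.4.3.2), and an unblinded IDMC watches these women (3.2).

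Much of this stands. It limits the likelihood and keeps the point small. It does not close the gap: 5.1.8 orders rescue without waiting, and haemoglobin checks and the IDMC act only after the second drug has been given.

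Two stronger readings might be inferred. One is that the protocol prescribes PQ after TQ. It does not; PQ enters only through local guidelines. The other is that the combination is shown to cause haemolysis, or that it materially biases the primary result. No data on TQ followed by PQ are given, the documents do not show that G6PD-normal subjects would reach the endpoint, and counting every haemoglobin fall in treated subjects, in both arms, is an ordinary safety convention.

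**Conclusion.** The gap is real and narrow. As written, a rule triggered by vomiting any product can lead a blinded site to give PQ to a subject who kept the full TQ dose, contrary to the interaction note in Appendix 5, and 4.4 and 5.1.8 disagree on when rescue is due. The conclusion assumes that some local guidelines would supply PQ and that some subjects vomit a later dose twice; the documents quantify neither. Cases will be few, and the concern rests mainly on moderately G6PD-deficient females, who are themselves limited in number. It justifies a short safety clarification, not a change to the design or the primary analysis.

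**What to change.** - **5.1.8 and 5.6.1.2.** Add: 'If the TQ/TQ-placebo tablets were retained, replace any lost CQ at once, but give no 8-aminoquinoline until the investigator has contacted the medical monitor and treatment has been established by code break. TQ subjects receive none unless malaria recurs; PQ subjects complete radical cure by local guideline.'
- **5.3.** List this case as a permitted code break.
- **4.4.** Cross-refer to 5.1.8 so that the two rules agree, with follow-up to Day 180.
- **RAP.** List any haemolysis events that follow a rescue anti-malarial. No extra analysis is needed. One that stopped at rescue and scored early-rescued subjects as event-free would cut across the rule in 13.6.3 that sets the endpoint to missing when haemoglobin data up to Study Day 17 are incomplete.

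The cost is a few sentences and one listing, with no extra visits. A few subjects are unblinded to their site, and a PQ subject's radical cure waits briefly while the code is broken.
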